##### *Hematology*

Complete blood count with platelet count and standard indices

##### *Chemistry*

Sodium, potassium, chloride, carbon dioxide, albumin, total protein, glucose, blood urea nitrogen, creatinine, uric acid, aspartate aminotransferase, alanine aminotransferase, gamma-glutamyl transpeptidase, creatine phosphokinase, alkaline phosphatase, total bilirubin, direct bilirubin, lactate dehydrogenase, calcium, and phosphorus.

##### *Coagulation Profile*

Prothrombin time or international normalized ratio, and partial thromboplastin time, also referred to as activated partial thromboplastin time.

### *Urinalysis*

Urine pH, glucose, protein, ketones, bilirubin, blood, urobilinogen, specific gravity, nitrite, and leukocytes by dipstick analysis or machine urinalysis. Urine microscopic examination will be performed if positive findings on dipsticks warrant further examination.

The frequency of patients with abnormal safety laboratory results will be tabulated by treatment received.

Shift tables of change in CTCAE grade of laboratory parameters from baseline to worst on-study values will be presented for hematology and clinical chemistry by QD/QW treatment received, if applicable. Shift tables of urinalysis results will be provided.

All laboratory data, including pregnancy test results, will be provided in data listings. A subset listing will be presented for all clinically significant laboratory values.

#### 4.5.5. Vital Signs

Vital signs will be measured according to the SoA ([Table 1](#)). Aside from those used in [REDACTED] evaluations, the actual value and change and percent change from baseline of temperature, HR, systolic blood pressure, diastolic blood pressure, and respiratory rate will be summarized descriptively by visit and QD/QW treatment received. Abnormal evaluations will be summarized in a table by QD/QW treatment received. A by-patient listing of all vital signs will be provided.

#### 4.5.6. Physical Examination and Comprehensive Skin Examination

Skin examination findings will be presented in a shift table, summarizing the shift from baseline to each visit for a given region by QD/QW treatment received. A by-patient listing of all skin examination findings will be provided.

Results from each component of the physical examination will be provided in shift tables, summarizing the shift from baseline to most abnormal result during follow-up. All physical examination findings will be presented in a data listing, including whether post-baseline findings were significant.

#### 4.5.7. Electrocardiogram

Electrocardiogram (ECG) results will be measured as shown in [Table 1](#) and overall interpretation will be summarized in a by-visit shift table by QD/QW treatment.

Continuous ECG data for each patient, including HR, PR interval, QRS duration, QT interval, and QT interval corrected with Fridericia's method will be provided in a summary table by treatment received and a by-patient data listing.

#### 4.5.8. Prior and Concomitant Medications

A prior medication is defined as any medication that was used and stopped before the start of the trial (Day -1 or before). A concomitant medication is defined as any medication with a stop date that is on or after the date of first dose of study drug.

Prior and concomitant medications will be coded using the WHO Drug Dictionary, version March 1, 2021, or later. Results will be tabulated by anatomic therapeutic class (ATC) and PT.

Prior and concomitant medications over the full study will be tabulated by QD/QW treatment group as well as by ATC level and PT in frequency tables. Patients with more than 1 medication at a given ATC level and PT will be counted only once in that category. If an end date is missing or the medication is ongoing, the medication will be included. Medications starting after the treatment withdrawal date will be listed but will not be classified or summarized. Partial dates will not be imputed.

The use of prior and/or concomitant medications will be included in a by-patient data listing.

#### 4.5.9. Columbia Suicide Severity Rating Scale

The C-SSRS will be measured as shown in the SoA ([Table 1](#)) according to the age of the patient (child <12 or adult  $\geq$ 12). Results of the C-SSRS will be provided in a shift table assessing shifts from the baseline most severe ideation to most severe ideation during follow-up. A by-patient listing including the ideation, intensity of ideation, behavior, and number of attempts will be provided.

#### 4.5.10. Patient Health Questionnaire-9

The Patient Health Questionnaire-9 will be measured as shown in the SoA ([Table 1](#)). The actual values, change, and percent change from baseline of the total scores will be summarized with descriptive statistics by visit. A by-patient listing of the results of the individual 9 questions will be provided.

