6.2. Patient Exclusion Criteria

A patient who meets any of the following criteria will be excluded from this trial.

- 1. $HbA_{1C} > 9.0\%$ at screening.
- 2. Has taken a medication that is approved to treat obesity (e.g., orlistat, lorcaserin, phentermine-topiramate, naltrexone-bupropion) within 3 months prior to starting the Run-in Period. Glucagon-like peptide-1 (GLP-1) receptor agonists being prescribed for the treatment of obesity are not allowed.
- 3. History of significant liver disease or liver injury, or a current liver assessment due to abnormal liver tests for an etiology other than nonalcoholic fatty liver disease (NAFLD). Thus, any underlying etiology besides NAFLD, including diagnosed nonalcoholic steatohepatitis (NASH), other causes of hepatitis, or history of hepatic cirrhosis is exclusionary, but the presence of NAFLD is not exclusionary.
- Moderate to severe renal dysfunction as defined by a glomerular filtration rate <30 mL/min (based upon the Chronic Kidney Disease Epidemiology Collaboration [CKD-EPI] creatinine equation 2021 from the National Kidney Foundation). In patients <18 years of age the Bedside Schwartz Equation should be used to calculate estimated glomerular filtration rate (eGFR).
- 5. Significant dermatologic findings relating to melanoma or pre-melanoma skin lesions (excluding non-invasive basal or squamous cell lesion), determined as part of comprehensive skin evaluation performed by the Investigator during screening. Any concerning lesions identified during the Screening Period will be biopsied and results

must be known to be benign prior to enrollment. If the pretreatment biopsy results are of concern, the patient should be excluded from the trial.

- 6. Diagnosis of schizophrenia, bipolar disorder, personality disorder, or other psychiatric disorders that the Investigator believes will interfere significantly with trial compliance. Neurocognitive disorders affecting ability to consent will not be disqualifying as long as an appropriate guardian able to give consent has been appointed.
- Clinically significant depression or suicidality as defined by: any suicidal ideation of type 4 or 5 on the C-SSRS, any lifetime history of a suicide attempt, or any suicidal behavior in the last month or a Patient Health Questionnaire-9 (PHQ-9) score of ≥15 during Screening in patients with no significant neurocognitive deficits.
- 8. Patient is not suitable, in the opinion of the Investigator, to participate in the trial.

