8.8.9. Suicidal Ideation and Depression Monitoring

As setmelanotide is considered to act through the central nervous system (CNS), a patient should be referred to a mental health professional (MHP) if he/she has:

- Any suicidal behavior
- Any suicidal ideation of type 4 or 5 on the C-SSRS
- A PHQ-9 score ≥ 10

A referral to a MHP should also be made if in the opinion of the Investigator it is necessary for the safety of the patient. If a patient's psychiatric disorder can be adequately treated with psychoand/or pharmacotherapy, then the patient, at the discretion of the MHP, should be continued in the trial.

In cognitively impaired patients or pediatric patients, the ability to complete the following Mental Health Assessment instruments as intended may be limited. If in the clinical opinion of the Investigator a specific patient cannot complete the instrument, the following strategies may be employed:

- Site staff may administer the questions directly to the patient or may ask for the information from a third party, such as a caregiver or family members, as appropriate.
- The Investigator may use his/her clinical judgment to skip any questionnaires that he/she feels are not appropriate for a specific patient.

Any deviation from the intended use of an instrument should be documented by the Investigator, along with the reason for the deviation. If the C-SSRS is not administered, the Investigator should document that the issue of suicidality was assessed clinically (e.g., discussion with caregivers).

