## 1.2. Study Design

### 1.2.1. Synopsis of Study Design

This study is designed to compare the safety, PK, and [REDACTED] of QD and QW formulations of setmelanotide, as well as to evaluate the safety and [REDACTED] of up to 6 months of QW setmelanotide administration in patients with BBS, biallelic PPL, or heterozygous PPL.

Eligible patients are those who have taken QD setmelanotide in Study RM-493-022 (referred to as the long-term extension [LTE] study) for at least 6 months with acceptable safety and tolerability, and who wish to continue with setmelanotide treatment. Such patients otherwise meet all inclusion and exclusion criteria. Approximately 30 patients will be targeted in 3 age groups as follows: approximately 20 patients  $\geq 18$  years old; approximately 6 patients  $\geq 12$  to  $< 18$  years old; and approximately 4 patients  $\geq 6$  to  $< 12$  years old at the time of study entry.

The study consists of a Screening Period for transition from the LTE study, a Run-in Period of up to 1 week of continuation on the patient's current dose level of QD setmelanotide (2, 2.5, or 3 mg), a 13-week double-blind phase in which the patients will be randomized to either QD or QW setmelanotide, a 13-week non-randomized open-label phase where all patients will receive open-label QW setmelanotide, and a 3-week follow-up period in which all patients will return to their run-in dose level of QD setmelanotide to prepare for re-enrollment into Study RM-493-022 or to resume the QD formulation in some other way.

Once informed consent is provided, patients will enter the Screening Period, during which they will be assessed for eligibility and complete all screening procedures as described in the Schedule of Assessments (SoA) ([Table 1](#)). During the Screening Period, patients will undergo medical evaluation and other study procedures, [REDACTED]. To ensure continuity of treatment, informed consent for this study will be obtained and eligibility of the patient will be confirmed before the patient is withdrawn from the LTE study.

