#### **3.2. General Methods**

All data listings that contain an evaluation date will contain a relative study day (Rel Day). Pre-treatment and on-treatment study days are numbered relative to the day of the first dose of study vaccine which is designated as Day 1. The preceding day is Day -1, the day before that is Day -2, etc. The last day of study medication is designated with an “L” (e.g., Day 14L). Post-treatment study days are numbered relative to the last dose and are designated as Day 1P, Day 2P, etc.

All output will be incorporated into Microsoft Word or Excel files, or Adobe Acrobat PDF files, sorted and labeled according to the International Conference on Harmonisation (ICH) recommendations, and formatted to the appropriate page size(s).

Tabulations will be produced for appropriate demographic, baseline, [REDACTED] PK, and safety parameters. For categorical variables, summary tabulations of the number and percentage of patients within each category (with a category for missing data) of the parameter will be presented. For continuous variables, the number of patients, mean, median, standard deviation (SD), minimum, and maximum values will be presented. Summarizations will be created for the groups of setmelanotide, genetic subgroups, and age groups.

This study is primarily descriptive in nature; therefore, there are no formal statistical hypothesis tests planned. Data will be presented by patient and summarized by QD/QW as well as genetic subgroup or by age group depending on the analysis. Summary statistics will be presented, as well as confidence intervals (CIs) on selected parameters, as described in the sections below.

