#### **3.4. Baseline Definitions**

For all [REDACTED] analyses, baseline will be defined as the following: the last value prior to randomization in the 13-week double-blind period.

For safety parameters including key laboratory (e.g., hematology and chemistry) data, the last value obtained prior to the first dose of setmelanotide or placebo in RM-493-037 will be used as the baseline. For the C-SSRS analysis, the baseline assessment that was collected at the beginning of the index study [REDACTED] should continue to be used as the baseline for this study.

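### PHQ-9 percent change has no rule for a baseline of 0, and no planned summary counts patients crossing the referral threshold of 10

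*SAP*

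**What the plan says.** SAP 4.5.10 plans two PHQ-9 outputs.

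- Table: "The actual values, change, and percent change from baseline of the total scores will be summarized with descriptive statistics by visit".
- Listing: "A by-patient listing of the results of the individual 9 questions will be provided". The total score is not named as part of it.

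SAP 3.2 fixes the statistics: "For continuous variables, the number of patients, mean, median, standard deviation (SD), minimum, and maximum values will be presented". SAP 3.4 sets the baseline for safety parameters: "the last value obtained prior to the first dose of setmelanotide or placebo in RM-493-037 will be used as the baseline". By the schedule, for the PHQ-9 that is the predose score on the first Run-in day (Visit 2), or else Screening.

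The protocol uses two PHQ-9 cut-offs. Section 6.2 excludes a "score of ≥15 during Screening in patients with no significant neurocognitive deficits". During the trial, Section 8.8.9 lists "A PHQ-9 score ≥ 10" among the triggers for referral to a mental health professional, and footnote 21 of the schedule repeats it in both documents.

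Two other safety measures get a baseline-to-worst shift table. For the C-SSRS, SAP 4.5.9 says: "Results of the C-SSRS will be provided in a shift table assessing shifts from the baseline most severe ideation to most severe ideation during follow-up". For hematology and chemistry, SAP 4.5.4 plans shifts in CTCAE grade from baseline to the worst value. The PHQ-9 gets neither a shift table nor a count at 10. Neither document states how percent change is handled when baseline is 0, and SAP 3.10 in general imputes nothing.

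**The concern.** The PHQ-9 total can be 0, and eligibility sets no lower limit on it. A patient with baseline 0 has no percent change, so the percent-change rows describe a subset chosen by its baseline score, with no statement that this has happened. Within that subset the statistic ranks changes badly, because a small rise from a very low score outweighs a larger rise that reaches the level at which the protocol acts.

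Separately, the question a safety reader would ask is how many patients rose from below 10 to 10 or more, and in which group. The protocol monitors mood because the drug is considered to act through the central nervous system, and 10 is the only PHQ-9 value that triggers action during the trial. With about 30 patients, one or two such crossings barely move a mean, and a per-visit maximum describes one patient only.

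**Working it through.** There is no stated figure to reproduce: the documents give no PHQ-9 distribution and no calculation for this output.

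**Inputs.** Planned size, SAP 1.2.1: "Approximately 30 patients will be targeted in 3 age groups as follows", with 20 + 6 + 4 = 30, so about 15 per arm at 1:1. Referral threshold 10 (Protocol 8.8.9). Admissible Screening scores 0 to 14 for patients without significant neurocognitive deficits (Protocol 6.2). The share s scoring 0 at baseline is not given; it is assumed to lie between 10% and 50%.

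**1. Percent change, 100 × (post − baseline) / baseline.**

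| Baseline to post | Change | Percent change | Crosses 10? |
|---|---|---|---|
| 0 to 10 | +10 | undefined | yes |
| 1 to 3 | +2 | 100 × 2/1 = +200% | no |
| 1 to 5 | +4 | 100 × 4/1 = +400% | no |
| 8 to 12 | +4 | 100 × 4/8 = +50% | yes |
| 9 to 10 | +1 | 100 × 1/9 = +11% | yes |

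**2. Patients missing from the percent-change rows, N × s.** For N = 30: 30 × 0.10 = 3 up to 30 × 0.50 = 15. Per arm of 15: 1.5 to 7.5. The chance of at least one baseline zero among 30 is 1 − (1 − s)^30, which is 1 − 0.9^30 = 0.96 at s = 10% and higher above that.

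**3. Which rows keep a new case.** Constructed data, for illustration only: 30 patients with baseline scores 0 (nine patients), 1 (four), 2 (four), 3 (four), 4 (three), 6 (three), 8 (two) and 11 (one). One patient goes from 0 to 12; the rest do not change.

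| Row | n | Result |
|---|---|---|
| Actual score | 30 | mean 81/30 = 2.7 at baseline, 93/30 = 3.1 after; maximum 11, then 12 |
| Change | 30 | mean 12/30 = +0.4, median 0, maximum +12 |
| Percent change | 21 | mean 0%, maximum 0% |
| Shift <10 to ≥10 (not planned) | 30 | 1 patient |

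The new case is absent from the percent-change row and visible in the change row as the maximum. If the patient at 11 is instead at 14 throughout, the maximum actual score is 14 at both times and hides the new case; the maximum change still shows +12. In neither version does a planned summary row give the number of patients who crossed 10.

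**The case against.** A reader might infer that new-onset depression disappears from the PHQ-9 table. The documents do not support that. The same sentence of SAP 4.5.10 also plans actual values and absolute change, both defined at baseline 0, and SAP 3.2 adds the number of patients and the maximum. A patient going from 0 to 10 leaves the percent-change rows only.

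A reader might also infer that many patients will score 0. That is an assumption. The stability required for entry is stability of dose, not of mood, and Screening scores up to 14 are allowed.

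Nor do the documents support saying that the QD/QW comparison is missing. SAP 4.5.10 names no split, but SAP 3.2 says in general that data are summarized by QD/QW, and the C-SSRS section also names none. The qualifier in SAP 3.2 about depending on the analysis leaves some looseness, which is a matter of wording.

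The remaining case against the point is one of weight. The study is descriptive, SAP 1.2.5.3 does not list the PHQ-9 among the safety endpoints, referral is triggered patient by patient at the visit, and in about 30 patients the listing can be read line by line. All of that stands, and it keeps the point small. It does not supply the count. The listing as described gives nine item results that a reader would have to add up, and Protocol 8.8.9 requires referral at 10 without saying that such a score is recorded as an adverse event, so the adverse event tables need not capture it.

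**Conclusion.** The point holds as a minor reporting gap. Two statements rest on the documents alone: percent change is planned for a score that may be 0 with no rule for that case, and no summary row gives the number of patients moving from below 10 to 10 or more. The size of the first, 3 to 15 of about 30 patients, rests on the assumed 10% to 50% with baseline 0. The second needs no assumption, and it matters slightly more because patients may enter at 10 to 14, so high scores during the trial mix old and new cases. No trial conclusion depends on this table.

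**What to change.** In SAP 4.5.10:

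1. Delete percent change. Keep actual value and change by visit.
2. Add a shift table of baseline (the SAP 3.4 safety baseline) in categories <10, 10-14 and ≥15 against the highest post-baseline score in the same categories: by randomized arm for the double-blind phase, and by randomized group for the open-label QW phase. Three categories separate patients who entered at 10 to 14 from new crossings and show worsening among them. Keep ≥15 at baseline, because the exclusion applies at Screening and not to patients with significant neurocognitive deficits.
3. State which visits feed each phase. By the protocol schedule the double-blind scores are Weeks 5, 9 and 14 (predose) and the open-label scores are Weeks 18, 22 and 27 (predose). The Day 1 predose score falls after the safety baseline but before randomized drug, so it should not count toward an arm.
4. Show a missing category, since Protocol 8.8.9 lets the investigator skip the questionnaire.
5. Include the total score in the by-patient listing.
6. Name the QD/QW split, as a clarification only.

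The cost is SAP wording and one small table. It uses data already collected.

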#### 4.5.11. Anti-RM Antibody

Anti-RM Antibody will be measured as shown in the SoA ([Table 1](#)). A by-patient listing, including the date of the assessment and result, will be provided.

## **5. CHANGES TO PLANNED ANALYSES**

All changes from procedures outlined in the protocol and procedures outlined in this SAP will be summarized in the CSR. Decisions to deviate from planned analyses will be documented at the time they are made.

If any modifications in the experimental design, dosages, parameters, patient selection, or any other sections of the protocol are indicated or required, the Investigator will consult with the Sponsor before such changes are instituted. Modifications will be accomplished through formal amendments to this protocol by the Sponsor and approval from the appropriate IRB or IEC.

